## Study Protocol

The purpose of this study is to expand upon a previous study of maternal addiction, by conducting a randomized, double-blinded, placebo controlled, crossover study of intranasal oxytocin (OT) on maternal brain responses. 150 mothers from the University of Iowa and the Yale Child Study Center will be enrolled (75 with a history of drug addiction and 75 matched control mothers), along with their 2 to 12-month-old infants, to participate in four study visits over a two-month period.

**Oxytocin administration and neuroimaging procedures.** In this double-blinded placebo-controlled crossover challenge of intranasal OT, maternal brain responses to infant face cues and cries were assessed between participants on receiving either the active (OT) or the inactive (placebo) nasal spray prior to one of two fMRI scanning sessions. Participants, investigators and data analysts were blinded to the identity of the OT and placebo sprays. Infant face images were presented during each scanning session. Specifically, infant face images were presented from each of the four following face conditions: the mother's own infant's face (happy and sad) and an unknown infant's face (happy and sad).

Current smokers were allowed the opportunity to smoke 60 min prior to the scanning session, to avoid any confounding effects of acute nicotine intoxication or withdrawal. All participants will take a urinary pregnancy test prior to the start of the visit. If a mother tested positive, she was excluded from the study due to theoretical concerns about effects of OT and MRI exposure on the pregnancy. The urine sample was used to screen for recent drug use, using the RediCup 5 drug test (for amphetamines, cocaine, marijuana, opioids and benzodiazepines).

The mothers self-administered a dose of either OT (2 puffs per nostril [6 IU per puff] = 24 IU total) or the placebo spray on each of two fMRI scanning visits, with a randomized order of administration. A stopwatch was started at the moment the participants began intranasal administration, so that the fMRI session began around 50 minutes later. Just prior to drug administration, the mother completed the Positive and Negative Affect Scale (PANAS), to rate her current emotions compared to 40 min later. During the 50-minute delay until scanning, the mother had a breath alcohol and CO (for cigarette usage) test, and completed a series of questionnaires, and demographic information was updated. Fifty minutes after the administration of the nasal spray, the mother participated in the imaging session, passively viewing own and unknown infant faces, and listening to infant cries.

**fMRI parameters.** Using an event-related fMRI design, randomly presented images were viewed for 2 seconds, with a random inter-stimulus interval between 4 and 14 sec. The infant face images were equally divided into 2 affect groups – happy or sad (own-happy [OH], own-sad [OS], unknown-happy [UH], unknown-sad [US]). The intensity of happy and sad affect will be balanced between the “own” and “unknown” faces. Each participant was presented with 4 fMRI runs of 38 different stimulus-trials each (2 catch trials and 6 trials each of OH, OS, UH, US, OC, UC), or 152 trials in all. For the catch trials, participants were asked to press a button when seeing and hearing a bell. The following steps were taken to avoid order-effects. Each run contained all 38 stimulus-trials in a different pseudorandom order that is unique and fixed for that run throughout the study. The order of fMRI runs were randomized (e.g. 1-2-3-4, 2-4-3-1, etc.) in a different sequence for each participant, but consistent across both scanning visits.

All imaging was performed using a 3 Tesla MRI scanner. Visual images were generated using a computer controlled LCD projector, and presented to the mother via an overhead mirror display. Regional brain activation was assessed by measuring changes in blood-oxygen-level-dependent functional MRI signal (BOLD-fMRI). Participants participated in whole-brain functional runs of around 185 scans each (multiband imaging with a factor of 6; 52 slices; TR 1000 msec; TE 30 msec; flip angle, 65 degrees; 64 x 64 matrix [in plane resolution]; field of view [FOV] 220 mm; slice thickness 2.4 mm; gap thickness 2.4 mm). High-resolution T1-weighted structural images (166 slices, in plane resolution 256 x 256; FOV 245 mm; slice thickness 1 mm) were also acquired. After the scanning session, each mother rated each of the face images on how they thought the infant was feeling, as well as their own feelings of pleasure or arousal, using an adaptation of the Self-Assessment Manikin.

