## Statistical Analysis Plan

A mixed effects model with random intercepts was run in R (version 4.2.2) using the lme4 package. Given the repeated measures design and the fact that there were incomplete data (i.e., not all subjects were in the OT and placebo condition), the mixed effects model provides a way of examining the effect of condition, controlling for the fact within-subjects nature of the study. For Hypothesis 1, which focuses on the effect of OT vs. placebo, on the condition variable was included in the model. For Hypothesis 2, group (addiction and controls) as well as condition was included. The interaction between group and condition was initially explored. Since there were no significant interaction effects, they were not included in subsequent analyses. P-values from the mixed-effects models were obtained using the Kenward-Roger approximation. Estimated marginal means and their standard errors were obtained from the model results using the R package “modelbased” (<https://cran.r-project.org/web/packages/modelbased/index.html>).

Anatomically-defined regions of interest (ROIs) based on the Harvard-Oxford Atlas were used to extract fMRI BOLD data representing the contrast of Happy own faces vs. Happy unknown faces or Sad own faces vs. Sad unknown faces. The contrasts represent data across all four task runs.

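### Controls are described as matched, but the Hypothesis 2 model uses no matching variable or pair term, which can cost power and leaves the group contrast open to bias under one specific missing-data pattern

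*Combined protocol and SAP*

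**What the plan says.** The opening paragraph of the Study Protocol sets the sample: "150 mothers from the University of Iowa and the Yale Child Study Center will be enrolled", made up of "75 with a history of drug addiction and 75 matched control mothers". The word matched is all the information given. The matching variables, and whether matching was individual or by frequency, are not stated.

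The first paragraph of the Statistical Analysis Plan gives the model: "A mixed effects model with random intercepts was run in R (version 4.2.2) using the lme4 package". The grouping unit of the intercept is not named, but its stated purpose is "controlling for the fact within-subjects nature of the study", which points to the mother and not to a matched pair. The fixed effects are given in one sentence: "For Hypothesis 2, group (addiction and controls) as well as condition was included". The group-by-condition interaction was looked at and dropped: "Since there were no significant interaction effects, they were not included in subsequent analyses". No matching variable, pair identifier, other covariate or site term appears.

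The same paragraph acknowledges that "there were incomplete data (i.e., not all subjects were in the OT and placebo condition". It does not give the number of mothers concerned or their split by group, and it has no rule for a control whose partner is missing.

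**The concern.** Only the order of OT and placebo is randomised. Addiction history is not, so the group comparison is observational, and matching is the one device described for making the two groups comparable. A model without the matching factors treats the groups as independent samples. Two things could follow.

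- **Precision.** If the factors used for matching predict the ROI contrast, matched mothers resemble each other. The difference between groups is then less variable than the model assumes, and a real group difference is harder to detect.
- **Balance.** Matching balances the groups as recruited, not the groups that supply usable scans. If losses disturb that balance, nothing in the model restores it.

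**Working it through.** **Plan's own figure.** 75 + 75 = 150, which agrees with the stated enrolment. The documents give no power, effect size, SD, alpha or dropout rate, so the sample size itself cannot be reproduced. A two-sided alpha of 0.05 is assumed throughout.

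**1. Standard error, if matching was one-to-one (75 complete pairs).** Let rho be the within-pair correlation of the mothers' mean contrasts, and work in units of the SD of that mean.

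- SE assumed by the model: sqrt(2/75) = 0.163.
- True SE: sqrt(2(1 − rho)/75).
- Ratio: 1/sqrt(1 − rho).
- True type I error: 2(1 − Φ(1.96/sqrt(1 − rho))).
- Power is evaluated at a difference of 0.46 SD, which 75 per group detects with 80% power when unpaired: (1.96 + 0.84) × 0.163 = 0.46.

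| rho (assumed) | true SE | SE ratio | type I error | power, unmatched model | power, matched model |
|---|---|---|---|---|---|
| 0 | 0.163 | 1.00 | 5.0% | 80% | 80% |
| 0.1 | 0.155 | 1.05 | 3.9% | 81% | 84% |
| 0.2 | 0.146 | 1.12 | 2.8% | 83% | 88% |
| 0.3 | 0.137 | 1.20 | 1.9% | 84% | 92% |
| 0.5 | 0.115 | 1.41 | 0.6% | 88% | 98% |

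If 80% power is instead attached to the matched analysis, unmatched power is Φ(2.80 − 1.96/sqrt(1 − rho)) = 77%, 73% and 68% at rho 0.1, 0.2 and 0.3.

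**2. Missing scans.** This was simulated with 4,000 runs per scenario: two scans per mother, within-mother correlation 0.3, and one binary matching factor balanced between groups with an effect of 0.3 or 0.6 SD (SD of a single scan within a factor level). There was no true group difference. All these values are assumptions.

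| Missingness per scan | bias, factor effect 0.3 / 0.6 (SD) | rejection rate |
|---|---|---|
| 20% in all mothers | 0.000 / −0.004 | 0.047 / 0.043 |
| 30% vs 10% by group only | 0.001 / 0.001 | 0.050 / 0.042 |
| 30% vs 10% by factor only | −0.004 / 0.002 | 0.051 / 0.038 |
| 50% in addiction mothers with the factor, 10% elsewhere | −0.030 / −0.072 | 0.047 / 0.068 |
| 70% in that cell, 10% elsewhere | −0.063 / −0.127 | 0.072 / 0.111 |

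Adding the factor as a fixed effect brought the bias to at most 0.006 SD in absolute value in every scenario.

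**3. Hand check of one entry (50% in one cell, factor effect 0.6).** The between-mother variance seen by the unadjusted model is 0.3 + 0.6²/4 = 0.39.

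- A mother with two scans has weight 1/(0.39 + 0.35) = 1.351; with one scan, 1/(0.39 + 0.70) = 0.917.
- Mean weight of addiction mothers with the factor: 0.25 × 1.351 + 0.50 × 0.917 = 0.796. Without it: 0.81 × 1.351 + 0.18 × 0.917 = 1.259.
- The factor's weighted share among addiction mothers is 0.796/(0.796 + 1.259) = 0.387, against 0.5 in controls.
- Bias: 0.6 × (0.387 − 0.5) = −0.068, in line with the simulated −0.072.

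The same reasoning explains the null rows. Loss by group alone leaves the factor's share at 0.5 in each group, and loss by factor alone shifts it equally in both.

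**The case against.** A reader might infer that the plan's standard error is simply wrong, or that ignoring the matching produces false positives. The documents do not support either reading. The formula in step 1 needs one-to-one pairs and a non-zero correlation, and the documents state neither. The outcome is already an own-minus-unknown contrast within each mother, which may remove much of the stable between-mother variation, and nothing shows that the matching factors predict it. With positive correlation the test errs on the safe side. How large the power loss looks also depends on where 80% is anchored: at 0.46 SD the unmatched model never falls below 80%. All of this stands.

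A reader might also infer that the matching is undone once any scan is missing. That does not follow. The SAP describes mothers lacking one condition, and the mixed model keeps them, although with less weight. Broken pairs are not bias in themselves. If 10% of mothers in each group gave no usable scan (an assumption), about 75 × 0.9² = 61 pairs would stay complete, yet random loss keeps the groups balanced in expectation. Bias needs missingness that depends jointly on group and a prognostic matching factor, and the documents give no evidence on this either way.

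Three further points stand. The protocol also lets smokers smoke 60 minutes before the scan to limit acute nicotine effects, so matching is not the only step taken against confounding. Hypothesis 2 is never spelled out; if its target is the group difference in OT response, a mother-level covariate entered as a main effect, or a pair intercept, largely cancels for mothers with both scans, and the figures above concern only the group main effect. Finally, the SAP already reports a result for the interaction, so swapping in a new headline model now would be a post hoc change.

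None of this answers the central point: a non-randomised comparison that was matched by design is analysed as if it were unmatched.

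**Conclusion.** The concern holds in a conditional form. The model described for Hypothesis 2 leaves out the matching, and the documents do not give the matching variables that a reader would need to judge the consequence.

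- **Standard error of the group main effect.** Under one-to-one matching it is too large by about 5%, 12% and 20% at assumed rho of 0.1, 0.2 and 0.3, with no error at rho = 0. The consequence is a conservative test and, at 0.46 SD, a loss of about 3, 5 and 8 percentage points of power.
- **Bias.** It is negligible (at most 0.004 SD) when missingness is uniform, follows group alone or follows the factor alone. It is 0.03 to 0.13 SD in the joint-dependence scenarios, where 50% or 70% of scans are lost in one cell.
- **Scope.** Only the group contrast is concerned. The within-mother OT versus placebo effect of Hypothesis 1 does not depend on the matching.

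The correlations, factor effects, within-mother correlation and missingness rates are all assumed; the documents supply none of them.

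**What to change.** 1. State the matching variables and whether matching was individual (with its ratio) or by frequency.
2. Add those variables as fixed effects to the Hypothesis 2 model. This suits either type of matching and still adjusts when a partner or a scan is missing.
3. Add a random intercept for pair, above the mother intercept, only if matching was one-to-one.
4. Report the adjusted group effect beside the unadjusted one. If the group results are already known, label the adjusted model as added afterwards; it should not silently replace the model in the SAP.
5. Tabulate usable scans by group and by level of each matching variable, so that a reader can see whether the harmful missingness pattern is present.

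The cost is SAP wording, a refit and a few degrees of freedom. No new data are needed, provided the matching variables were recorded at recruitment, which the documents do not confirm.

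### The non-randomised Hypothesis 2 comparison is not adjusted for infant age (2 to 12 months), and the matching factors are not named, so the group effect may be biased or lose some precision

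*Combined protocol and SAP*

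**What the plan says.** - Study Protocol, opening paragraph: the sample is "75 with a history of drug addiction and 75 matched control mothers", enrolled "along with their 2 to 12-month-old infants". The matching factors are not listed here or anywhere else. Participation is described as "to participate in four study visits over a two-month period".
- Study Protocol, Oxytocin administration and neuroimaging procedures: the only thing randomised to a mother's treatment is the sequence of the two sprays ("with a randomized order of administration"). Addiction history is an observed characteristic.
- Statistical Analysis Plan: "A mixed effects model with random intercepts was run in R (version 4.2.2) using the lme4 package". The terms are then given: "For Hypothesis 2, group (addiction and controls) as well as condition was included". No covariate is named. On the group-by-condition term: "Since there were no significant interaction effects, they were not included in subsequent analyses". The same section acknowledges that some mothers lack data in one of the two conditions.
- Statistical Analysis Plan, last paragraph: the outcome is an ROI BOLD measure of "the contrast of Happy own faces vs. Happy unknown faces or Sad own faces vs. Sad unknown faces".

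**The concern.** With the interaction removed, what is left of Hypothesis 2 in the stated model is the group main effect, which compares different mothers. A random intercept handles the correlation between a mother's two sessions. It does not remove differences between mothers, so anything that differs between the groups and predicts the contrast is credited to addiction.

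Infant age is a natural candidate. It spans 10 months and must be known for every mother, because it defines who can enrol. It also sets the age of the face in the own-infant condition. The fMRI parameters paragraph says that own and unknown faces are balanced on intensity of affect. It says nothing about the age of the unknown infants, so subtracting one response from the other does not evidently cancel age. Nor is infant age an obvious consequence of addiction, as smoking or current drug use may be, so the usual worry about adjusting away part of the effect has little force.

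Two things are at stake. If infant age differs systematically by group, the group estimate may be biased. If it does not differ but does predict the contrast, its variation stays in the error term and the interval is wider than it need be.

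**Working it through.** There is no plan figure to reproduce. The documents give no alpha, power, effect size, SD or derivation of the 150, no infant-age distribution, and no correlation between infant age and the contrast. What follows is a sensitivity calculation.

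**From the documents:** 75 mothers per group; infant age 2 to 12 months; model terms group, condition and random intercept.

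**Assumed:** two-sided 5% test; SD of a mother's mean contrast set to 1; correlation *r* between infant age and that mean of 0 to 0.3; infant ages uniform over the range, so SD of age = 10/√12 = 2.89 months.

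**1. Unadjusted SE of the group effect.** √(2/75) = 0.163 SD.

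**2. Precision.** With the groups balanced on age, adjustment multiplies the SE by √(1 − r²):
- r = 0: 1.000, no gain
- r = 0.1: 0.995, a reduction of 0.5%
- r = 0.2: 0.980, a reduction of 2.0%
- r = 0.3: 0.954, a reduction of 4.6%

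An effect of 0.457 SD has 80.0% power unadjusted. Adjusted power is 80.4%, 81.6% and 83.6% at r = 0.1, 0.2 and 0.3.

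**3. Cross-check in the two-session model.** The variance of a mother's mean is ICC + (1 − ICC)/2. At ICC 0.4 this is 0.4 + 0.3 = 0.7. If age explains 16% of the between-mother part, the adjusted variance is 0.4 × 0.84 + 0.3 = 0.636, and the SE ratio is √(0.636/0.7) = 0.953. That matches r = 0.3 above, so r = 0.3 already credits infant age with about a sixth of the stable variation between mothers.

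**4. Bias from a systematic gap.** Bias = r × gap/2.89. The error rate is the two-sided normal probability of rejection after a shift of bias/0.163 standard errors.

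| Gap in mean infant age | r = 0.1 | r = 0.2 | r = 0.3 |
|---|---|---|---|
| 1 month | 0.035 SD, 5.5% | 0.069 SD, 7.1% | 0.104 SD, 9.8% |
| 2 months | 0.069 SD, 7.1% | 0.139 SD, 13.6% | 0.208 SD, 24.7% |
| 3 months | 0.104 SD, 9.8% | 0.208 SD, 24.7% | 0.312 SD, 48.0% |

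At r = 0, or with no gap, the bias is zero and the rate is 5%.

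**5. What chance alone would produce.** If the two groups had the same infant-age distribution, the SE of the gap would be 2.89 × 0.163 = 0.47 months. A 1-month gap is 1/0.47 = 2.1 such standard errors. It would be unusual by chance, but is possible if recruitment differs between the groups.

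**6. The price of adjusting when there is a gap.** With equal groups and a gap of d age-SDs, the adjusted SE is also multiplied by √(1 + d²/4). For 1 month, d = 1/2.89 = 0.346 and the factor is √1.03 = 1.015. The net ratio is then 0.980 × 1.015 = 0.994 at r = 0.2 and 0.954 × 1.015 = 0.968 at r = 0.3. With a gap of that size, the reason to adjust is bias, not precision.

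**The case against.** The case on the other side is substantial, and much of it stands.

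- **No demonstrated link.** Nothing in the documents shows that infant age predicts the own-minus-unknown contrast or that it differs by group. A reader might infer that the group effect is in fact biased or imprecise; the documents support only that it may be.
- **Matching.** Controls are matched. If infant age was a factor, the imbalance argument largely falls away. This stands as far as it goes, but because the factors are unnamed, nobody can tell whether it applies. If age was matched and predicts the contrast, a model without it still gives up some precision.
- **Chance imbalance.** The unadjusted SE already allows for chance gaps, so the unconditional 5% rate is intact. This stands: the raised error rates above apply only to a systematic gap.
- **Larger magnitudes.** A reader might infer an SE reduction as large as 13%. That needs, for example, a single-session correlation of 0.4 with an ICC of 0.3, so that infant age explains 0.16/0.30 = 53% of stable between-mother variance, and both sessions for everyone. The first is implausible, and the second conflicts with the incomplete data that the SAP reports.
- **The model is reported as already run.** Substituting another model now would be a post-hoc choice. This stands, and governs how the adjusted result should be presented.
- **Scope of Hypothesis 2.** Its wording is not given. If it asks whether group modifies the oxytocin effect, an additive age effect largely cancels within mothers. But that interaction was dropped, which leaves the group main effect. Hypothesis 1 is mainly a within-mother comparison and is little affected.
- **Choice of covariate.** Site is also missing from the model, although there are two institutions. That is a fair remark, but it does not make the omission of infant age harmless.

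Nor do the documents show that infant age was considered and deliberately left out; they are silent on it.

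**Conclusion.** The point holds in a limited form. A non-randomised between-mother comparison is reported from a model with no adjustment for infant age, a baseline value known for every mother and tied to the own-face stimulus, and the matching that might have dealt with it is not described.

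The consequence depends on which case applies. If infant age was matched, the main loss is precision: 0 to about 5% of the SE for correlations of 0 to 0.3. If it was not matched and the groups differ systematically by 1 month, the group effect shifts by about 0.07 to 0.10 SD at correlations of 0.2 to 0.3, and a nominal 5% test rejects a true null about 7 to 10% of the time. With no correlation or no gap there is no bias.

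These sizes rest on 75 analysed mothers per group, uniform infant ages and the assumed correlations, none of which the documents settle. They do not support a statement that the Hypothesis 2 result is wrong.

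**What to change.** - Fit Hypothesis 2 as group + condition + infant age in months at the first scan visit (continuous) + random intercept for mother.
- Name the factors on which controls were matched, and include them in the same model.
- Report mean infant age by group next to the group estimate, so that a reader can see which case applies.
- If the model without infant age has already been run, keep its result, report the adjusted estimate beside it, and label the adjusted analysis as added later.

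No new data should be needed for infant age. The cost is one degree of freedom, plus those for any matching factors, and a covariate that would be specified after the stated model. If the groups differ in infant age, there is also a small widening of the SE, about 1.5% for a 1-month gap before any gain from explained variance.
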